2.3.5. Site Inspections

Site visits will be conducted by the Sponsor or an authorized representative for inspection of study data, participants' medical records, and eCRFs. The Investigator will permit national and local Health Authorities, Sponsor monitors, representatives, and collaborators, and the IRBs/ECs to inspect facilities and records relevant to this study.

3. ADMINISTRATIVE STRUCTURE

Not applicable.

4. STUDY AND SITE CLOSURE

The Sponsor (or designee) has the right to close the study site or terminate this study at any time. Reasons for terminating the study may include, but are not limited to, the following:

- The incidence or severity of AEs in this or other studies indicates a potential health hazard to participants.
- Participant enrollment is unsatisfactory.
- Emerging data and/or prioritization of assets.

If general study stopping criteria are met, the study will be paused and the Sponsor will conduct a full review of all available safety data. The study will resume if the Sponsor and Investigator agree and after informing and receiving agreement from relevant Health Authorities and Ethics Committees.

If the study is placed on hold, or if the Sponsor decides to discontinue the study or the development program, the Sponsor shall promptly inform the Investigators, the IRBs/ECs, the health authorities, and any contract research organizations used for the study of the reason for termination or suspension, as specified by the applicable regulatory requirements. The Investigators shall promptly inform the participants and should ensure appropriate participant therapy and/or follow-up.

Study sites will be closed upon study completion. A study site is considered closed when all required documents and study supplies have been collected and a study site closure visit has been performed.

The Investigator may initiate study site closure at any time, provided there is reasonable cause and sufficient notice is given in advance of the intended termination.

Reasons for the early closure of a study site by the Sponsor or Investigator may include but are not limited to:

- Failure of the Investigator to comply with the protocol, the requirements of the IRB/IEC or local Health Authorities, the Sponsor's procedures, or GCP guidelines.
- Inadequate recruitment of participants by the Investigator.
- Discontinuation of further study treatment development.

Appendix 2

Adverse Events: Definitions and Procedures for Evaluating, Follow-up and Reporting

1. DEFINITION OF ADVERSE EVENTS

According to the E2A International Council for Harmonisation (ICH) guideline for Good Clinical Practice (GCP), an **adverse event** (AE) is any untoward medical occurrence in a participant or clinical investigation participant administered a pharmaceutical product and that does not necessarily have to have a causal relationship with this treatment.

An AE can therefore be:

- Any unfavorable and unintended sign (including an abnormal laboratory finding), symptom, or disease temporally associated with the use of a medicinal product, whether or not considered related to the medicinal product.

Events Meeting the AE Definition:

- Deterioration in a laboratory value (hematology, clinical chemistry, or urinalysis) or other clinical test (e.g., ECG, x-ray) that is associated with symptoms or leads to a change in study treatment or concomitant treatment or discontinuation from study treatment (see [Appendix 3, Section 4](#)).
- Exacerbation of a chronic or intermittent preexisting condition, including either an increase in frequency and/or intensity of the condition.
- New conditions detected or diagnosed after study treatment administration even though it may have been present before the start of the study.
- AEs that are related to a protocol-mandated intervention, including those that occur prior to assignment of study treatment (e.g., screening invasive procedures such as biopsies).

Events NOT Meeting the AE Definition:

- Any clinically significant abnormal laboratory findings or other abnormal safety assessments that are associated with the underlying disease, unless judged by the Investigator to be more severe than expected for the participant's condition.
- The disease/disorder being studied or expected progression, signs, or symptoms of the disease/disorder being studied, unless more severe than expected for the participant's condition.
- Medical or surgical procedure (e.g., endoscopy, appendectomy): The condition that leads to the procedure is an AE.
- Situations where an untoward medical occurrence did not occur (social and/or convenience admission to a hospital).
- Anticipated day-to-day fluctuations of preexisting disease(s) or condition(s) present or detected at the start of the study that do not worsen.

2. DEFINITION OF SERIOUS ADVERSE EVENTS

If an event is not an AE per definition above, then it cannot be an SAE even if serious conditions are met (e.g., hospitalization for signs/symptoms of the disease under study, death due to progression of disease).

An SAE is defined as any untoward medical occurrence that at any dose:

- **Results in death.**
- **Is life-threatening.**

The term "life-threatening" in the definition of "serious" refers to an event during which the participant was at risk of death at the time of the event; it does not refer to an event which hypothetically might have caused death if it was more severe.

- **Requires inpatient hospitalization or prolongation of existing hospitalization** (see [Appendix 3](#)).

In general, hospitalization signifies that the participant has been detained (usually involving at least an overnight stay) at the hospital or emergency ward for observation and/or treatment that would not have been appropriate in the physician's office or outpatient setting. Complications that occur during hospitalization are AEs. If a complication prolongs hospitalization or fulfills any other serious criteria, the event is serious. When in doubt as to whether "hospitalization" occurred or was necessary, the AE should be considered serious.

- **Results in persistent or significant disability/incapacity**

Disability means substantial disruption of the participant's ability to conduct normal life functions.

This definition is not intended to include experiences of relatively minor medical significance such as uncomplicated headache, nausea, vomiting, diarrhea, influenza, and accidental trauma (e.g., sprained ankle) which may interfere with or prevent everyday life functions but do not constitute a substantial disruption.

- **Is a congenital anomaly/birth defect.**

- **Other significant events:**

Medical or scientific judgment should be exercised in deciding whether SAE reporting is appropriate in other situations such as important medical events that may not be immediately life-threatening or result in death or hospitalization but may jeopardize the participant or may require medical or surgical intervention to prevent one of the other outcomes listed in the above definition. These events should usually be considered serious.

Examples of such events include

- elevated ALT or AST ($>3\times$ ULN and $>3\times$ baseline) in combination with either an elevated total bilirubin ($>2\times$ ULN) or clinical jaundice in the absence of cholestasis or other causes of hyperbilirubinemia (potential Hy's law).

3. RECORDING OF ADVERSE EVENT AND/OR SERIOUS ADVERSE EVENT

When an AE/SAE occurs, it is the responsibility of the Investigator to review all documentation (e.g., hospital progress notes, laboratory reports, and diagnostics reports) related to the event.

The Investigator will then record all relevant AE/SAE information in the electronic case report form (eCRF).

It is **not** acceptable for the Investigator to send photocopies of the participant's medical records to Medical Monitor in lieu of completion of the eCRF.

There may be instances when copies of medical records for certain cases are requested by the Medical Monitor. In this case, all participant identifiers, with the exception of the participant number, will be redacted on the copies of the medical records before submission to the Medical Monitor.

The Investigator will attempt to establish a diagnosis of the event on the basis of signs, symptoms, and/or other clinical information. Whenever possible, the diagnosis (not the individual signs/symptoms) will be documented as the AE/SAE.

3.1. ASSESSMENT OF SEVERITY

The terms "severe" and "serious" are not synonymous. Severity refers to the intensity of an AE (rated as mild, moderate, severe, or according to a predefined grading criteria) (Division of AIDS Table for Grading the Severity of Adult and Pediatric Adverse Events [DAIDS]); the event itself may be of relatively minor medical significance (such as severe headache without any further findings).

Severity and seriousness need to be independently assessed for each AE recorded on the eCRF.

SAEs are required to be reported by the Investigator to the Sponsor immediately (i.e., no more than 24 hours after learning of the event).

The adverse event severity grading scale for the DAIDS (v2.1) will be used for assessing severity for adverse events. [Table 1](#) will be used for assessing severity for AEs that are not specifically listed in the DAIDS.

Table 1 DAIDS Adverse Event Severity Grading Scale for Events Not Specifically Listed in DAIDS Toxicity Grading Scale

| Grade | Description |
|-------|---|
| 1 | Mild symptoms causing no or minimal interference with usual social & functional activities with intervention not indicated |
| 2 | Moderate symptoms causing greater than minimal interference with usual social & functional activities with intervention indicated |
| 3 | Severe symptoms causing inability to perform usual social & functional activities with intervention or hospitalization indicated |
| 4 | Potentially life-threatening symptoms causing inability to perform basic self-care functions with intervention indicated to prevent permanent impairment, persistent disability, or death |
| 5 | Death |

Abbreviation: DAIDS = Division of AIDS

Note: Regardless of severity, some events may also meet seriousness criteria. Refer to definition of a serious adverse event (see above). DAIDS v2.1 grading scale is available at: <https://rsc.niaid.nih.gov/sites/default/files/daidsgradingcorrectedv21.pdf>. Developed by the DAIDS, National Institute of Allergy and Infectious Diseases, National Institutes of Health, U.S. Department of Health and Human Services.

3.2. ASSESSMENT OF CAUSALITY

Investigators should use their knowledge of the participant, the circumstances surrounding the event, and an evaluation of any potential alternative causes to determine whether or not an AE is considered to be related to the study treatment, indicating "yes" or "no" accordingly. The following guidance should be taken into consideration:

- Temporal relationship of event onset to the initiation of study treatment.
- Course of the event, considering especially the effects of dose reduction, discontinuation of study treatment, or reintroduction of study treatment.
- Known association of the event with the study treatment or with similar treatments.
- Known association of the event with the disease under study.
- Presence of risk factors in the participant or use of concomitant medications known to increase the occurrence of the event.
- Presence of non-treatment-related factors that are known to be associated with the occurrence of the event.

For participant receiving combination therapy, causality will be assessed individually for each protocol-mandated therapy.

4. FOLLOW-UP OF AES AND SAEs

The Investigator is obligated to perform or arrange for the conduct of supplemental measurements and/or evaluations as medically indicated or as requested by the Medical Monitor to elucidate the nature and/or causality of the AE or SAE as fully as possible. This may include additional laboratory tests or investigations, histopathological examinations, or consultation with other health care professionals.

If a participant dies during participation in the study or during a recognized follow-up period, when possible the Investigator will provide the Sponsor with a copy of any post-mortem findings, including histopathology.

New or updated information will be recorded in the originally completed eCRF.

The Investigator will submit any updated SAE data to the Sponsor within 24 hours of receipt of the information.

5. IMMEDIATE REPORTING REQUIREMENTS FROM INVESTIGATOR TO SPONSOR

Certain events require immediate reporting to allow the Sponsor to take appropriate measures to address potential new risks in a clinical study. The Investigator must report such events to the Sponsor immediately; under no circumstances should reporting take place more than 24 hours after the Investigator learns of the event. The following is a list of events that the Investigator must report to the Sponsor within 24 hours after learning of the event, regardless of relationship to study treatment:

- SAEs
- AEs of special interest (AESI; see Section 8.3.6)
- Pregnancies (see Section 8.3.5)

The Investigator must report new significant follow-up information for these events to the Sponsor immediately (i.e., no more than 24 hours after becoming aware of the information). New significant information includes the following:

- New signs or symptoms or a change in the diagnosis.
- Significant new diagnostic test results.
- Change in causality on the basis of new information.
- Change in the event's outcome, including recovery.
- Additional narrative information on the clinical course of the event.

Investigators must also comply with local requirements for reporting SAEs to the local Health Authority and Institutional Review Board (IRB)/ethics committee (EC).

5.1 REPORTING REQUIREMENTS OF SERIOUS ADVERSE EVENTS AND ADVERSE EVENTS OF SPECIAL INTEREST

Events that Occur prior to Study Treatment Initiation

After informed consent has been obtained but prior to initiation of study treatment, only SAEs caused by a protocol-mandated intervention should be reported. The Clinical Trial Adverse Event/Special Situations Form provided to Investigators should be completed and submitted to the Serious Adverse Event Responsible immediately (i.e., no more than 24 hours after learning of the event).

Events that Occur after Study Treatment Initiation

For reports of SAEs and AESI (Section 8.3.6) that occur after initiation of study treatment (Section 8.3.1), Investigators should record all case details that can be gathered immediately (i.e., within 24 hours after learning of the event) on the appropriate Adverse Event of Special Interest/Serious Adverse Event eCRF form and submit the report via the electronic data capture (EDC) system. A report will be generated and sent to the Sponsor's Safety Risk Management department.

In the event that the EDC system is unavailable, the Clinical Trial Adverse Event/Special Situations Form provided to Investigators should be completed and submitted to the Serious Adverse Event Responsible immediately (i.e., no more than 24 hours after learning of the event).

Once the EDC system is available, all information will need to be entered and submitted via the EDC system.

Reporting of Post-Study Adverse Events and Serious Adverse Events

If the Investigator becomes aware of any other SAE occurring after the end of the AE reporting period, and if the event is believed to be related to prior study treatment, the event should be reported directly to the Sponsor or its designee, either by faxing or by scanning and emailing the Clinical Trial Adverse Event/Special Situations Form using the fax number or email address provided to Investigators.

6. SPECIAL SITUATIONS (ACCIDENTAL OVERDOSE OR MEDICATION ERROR)

Accidental overdose and medication error (hereafter collectively referred to as "special situations"), are defined as follows:

- Accidental overdose: Accidental administration of a drug in a quantity that is higher than the assigned dose.

- Medication error: Accidental deviation in the administration of a drug (e.g., wrong drug, expired drug, accidental overdose, underdose, wrong dosing schedule, incorrect route of administration).

After initiation of study drug, special situations associated with RO7565020/matching placebo and any associated AEs will be reported until 6 months after the final dose of study drug.

Special situations, regardless of whether they result in an AE, should be recorded on the Special Situations eCRF. If there are any associated AEs, each event should be recorded separately on the Adverse Event eCRF.

Special situations and any associated AEs should be reported within 30 days after the Investigator becomes aware of the situation. However, if an associated AE fulfills seriousness criteria or qualifies as an AE of special interest, both the event and the special situation should be reported to the Sponsor immediately (i.e., no more than 24 hours after the Investigator becomes aware of the event), as described in Section [5.1](#) of this appendix.

7. EXPEDITED REPORTING TO HEALTH AUTHORITIES, INVESTIGATORS, INSTITUTIONAL REVIEW BOARDS, AND ETHICS COMMITTEES

The Sponsor will promptly evaluate all SAEs and AESIs against cumulative product experience to identify and expeditiously communicate possible new safety findings to Investigators, IRBs/ ECs, and applicable Health Authorities on the basis of applicable legislation.

To determine reporting requirements for single AE cases, the Sponsor will assess the expectedness of these events through use of the reference safety information (RSI) in the documents listed below:

| Drug | Document |
|-------------------|---|
| RO7565020 | Investigator's Brochure RO7565020 |
| RO7565020 placebo | Investigator's Brochure RO7565020 |

The Sponsor will compare the severity of each event and the cumulative event frequency reported for the study with the severity and frequency reported in the applicable reference document.

Reporting requirements will also be based on the Investigator's assessment of causality and seriousness, with allowance for upgrading by the Sponsor as needed.

Appendix 3 **Procedures for Recording Adverse Events**

Investigators should use correct medical terminology/concepts when recording adverse events (AEs) on the Adverse Event electronic case report form (eCRF). Avoid colloquialisms and abbreviations.

Only one AE term should be recorded in the event field on the Adverse Event eCRF.

1. DIAGNOSIS VERSUS SIGNS AND SYMPTOMS

1.1. INFUSION REACTIONS/ INJECTION REACTIONS

AEs associated with the intravenous infusion or injection that occur during or within 24 hours after study treatment administration should be captured as individual signs and symptoms on the Adverse Event eCRF rather than as an overall diagnosis (e.g., record dyspnea and hypotension as separate events rather than a diagnosis of infusion-/ injection-related reaction or anaphylactic reaction).

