3. OBJECTIVES AND ENDPOINTS

The objectives and corresponding endpoints are provided in [Table 5](#).

Table 5 Objectives and Endpoints

| Objectives | Endpoints |
|--|--|
| Primary | |
| 
 • To assess the safety and tolerability: 
 ◦ following a single dose of RO7565020 administered subcutaneously (SC) or intravenously (IV) to healthy participants (Part 1a) and SC to virologically suppressed participants with chronic hepatitis B (CHB) (Part 2) ◦ following multiple doses of RO7565020 administered SC to healthy participants (Part 1b) and virologically suppressed participants with CHB (Part 3) | 
 • Frequency and severity of adverse events (AEs), including adverse events of special interest (AESI), serious adverse events (SAE), and treatment discontinuations due to AEs • Frequency of abnormal laboratory findings based on hematology, blood chemistry (including liver function tests), coagulation and urinalysis test results • Frequency of clinically significant abnormalities in ECGs and vital signs • Mean changes from baseline in vital signs (temperature, systolic and diastolic blood pressure, pulse rate, respiratory rate) over time |
| Secondary | |
| 
 • To investigate the serum pharmacokinetics of RO7565020: 
 ◦ following single-ascending doses of RO7565020 administered SC or IV to healthy participants (Part 1a) and SC to virologically suppressed participants with CHB (Part 2) ◦ following multiple doses of RO7565020 administered SC to healthy participants (Part 1b) and virologically suppressed participants with CHB (Part 3) | 
 • PK parameters of RO7565020: 
 ◦ Time to maximum concentration (t_{max}) ◦ Maximum serum concentration observed (C_{max}) ◦ AUC from Time 0 to time of last sampling point or last quantifiable sample, whichever comes first (AUC_{0-last}) ◦ AUC from Time 0 to infinity (AUC_{inf}) ◦ Terminal half-life ($t_{1/2}$) ◦ Volume of distribution (V_{ss}) and clearance (CL) (IV only) ◦ Apparent clearance (CL/F), apparent volume of distribution at terminal phase (V_z/F) (SC only) |

Table 5 Objectives and Endpoints (cont.)

| Objectives | Endpoints |
|---|---|
| Secondary (cont.) | |

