4.1.1.3 Stopping Rules Criteria

4.1.1.3.1 Cohort Stopping Rules

Part 1

Dose escalation will be stopped and dosing at a given level will be stopped if one of the following circumstances occurs in participants treated with RO7565020 within the same dose cohort:

- Severe non-serious adverse reactions (Grade 3 or above, as per Division of AIDS [DAIDS] grading, v2.1, considered to be related to RO7565020) in 2 or more participants receiving RO7565020 in the same cohort, independent of the system organ classes.
- Any serious adverse reaction in 1 participant (i.e., a serious AE [SAE] considered to be related to RO7565020).
- Grade 2 or above clinically significant laboratory abnormalities, vital sign change, or ECG change, of the same type in 3 or more participants receiving RO7565020 in the same cohort.
- Other findings, which at the discretion of the DDT, indicate that dose escalation or dosing at that dose level should be stopped.
- Dose escalation will also be stopped if increasing the dose does not result in a significant increase in serum exposure of RO7565020.

Parts 2 and 3

Dose escalation and dosing at a given level of RO7565020 will be temporarily halted if one of the following circumstances occurs. Dosing might be resumed if deemed appropriate following the DDT review of the available safety, PK, and PD data. Relevant reporting and discussion with relevant DDT personnel and the Institutional Review Board (IRB)/ Independent Ethics Committee (IEC) will take place before potential resumption of dosing.

- Severe non-serious adverse reactions (Grade 3 or above, as per DAIDS grading, v2.1, considered to be related to RO7565020) in 2 or more participants receiving RO7565020 in the same cohort, independent of the system organ classes
- Any serious adverse reaction in 1 participant (an SAE considered to be related to RO7565020)
- Other findings which, at the discretion of the DDT members, indicate that dose escalation or dosing at that level should be stopped

In case dose escalation is stopped, lower doses within the tolerated dose range could be investigated or a dose repeated in subsequent cohorts to increase the amount of data within this tolerated dose range.

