8.3.7 Management of Specific Adverse Events

Injection-site reactions or hypersensitivity reactions will be managed at the Principal Investigator's discretion with appropriate documentation that the treatment course was in reaction to evident findings (i.e., acetaminophen administered in response to documented fever or pain, graded use of antihistamine, glucocorticoids, or epinephrine for appropriately severe allergic findings, meperidine administered for documented rigors). If the participant experiences any suspected HBsAg-HBsAb immune complex mediated AEs (e.g., serum sickness; please refer to the [RO7565020 IB](#) for more information), an unscheduled sample will be collected (see [Table 9](#)), and the participant will be managed according to institutional practice at the Principal Investigator's discretion. No prophylactic treatments that could mask clinical findings that may emerge upon dosing with study drug will be administered without prior consultation with the Sponsor's Medical Monitor. If a study drug-related anaphylactic or serious hypersensitivity reaction occurs, administration of RO7565020 should be stopped immediately and permanently discontinued.

In the case of a possible event of ALT elevation or virological breakthrough during study treatment in Parts 2 and 3 in participants with CHB, please consider the following recommended guidelines for management of specific AEs ([Table 9](#)).

Table 9 Guidelines for Managing Specific Adverse Events

| Event | Action to Be Taken |
|--|---|
| Injection-site reaction | 
Manage according to institutional practice. |
| Infusion-related reaction | 
If the severity of the event is Grade ≥ 2, collect unscheduled safety samples including ADA, complement activation, CRP, hematology, blood chemistry, and coagulation. |
| Hypersensitivity reactions | |
| Study drug-related anaphylactic or serious hypersensitivity reaction | 
Stop administration of RO7565020 immediately and permanently discontinue RO7565020.Manage according to institutional practice.Collect unscheduled safety samples including ADA, complement activation, CRP, hematology, blood chemistry, and coagulation. |
| For Parts 2 and 3 only (participants with CHB) | |

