9.4.2 Safety Analyses

All safety analyses will be based on the safety analysis set (see [Table 11](#)). Participants will be summarized by cohort. In addition, all study participants who are randomized to receive SC or IV placebo will be pooled as respective SC or IV placebo control groups, according to each part of the study.

The safety data, including AEs, injection-site reactions, reasons for withdrawal from study, laboratory data, ECG, concomitant medications, vital signs, and physical examination results will be listed and summarized descriptively. Marked abnormalities of laboratory data will be flagged. As appropriate, listings, summary tables and graphs (participant plot and/or mean plots) will be provided to describe safety and tolerability assessments.

Table 11 Safety Statistical Analysis Methods

| Endpoint | Statistical Analysis Methods |
|---------------------------|--|
| Adverse events | The original terms recorded on the eCRF by the Investigator for AEs will be coded by the Sponsor. AEs will be summarized by mapped term and appropriate thesaurus level. Frequency and severity of adverse events will be summarized. |
| Clinical laboratory tests | All clinical laboratory data will be stored on the database in the units in which they were reported. Laboratory test values will be presented in International System of Units (SI units) by individual outputs with flagging of abnormal results. Summary tables of absolute value and change from baseline over time will be displayed. Shifts in DAIDS grades v2.1 from baseline to the worst grade observed during treatment will be presented for selected laboratory parameters. For details on standard reference ranges and data transformation and the definition of laboratory abnormalities, see Appendix 4 . |
| Vital signs | Vital sign data will be presented with flagging of values outside the normal ranges and flagging of abnormalities. Mean changes from baseline and absolute value over time will be provided. |
| ECG data analysis | ECG data will be presented using appropriate outputs, as detailed in Section 9.4.2.1 . |
| Concomitant medications | The original terms recorded on the participants' eCRF by the Investigator for concomitant medications will be standardized by the Sponsor by utilizing a mapped term and appropriate drug dictionary level. Concomitant medications will be presented using appropriate outputs. |

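### Infusion, injection and anaphylactic reactions within 24 hours are to be recorded as separate signs, against the general recording rule and with no link described, so the planned tables cannot show how many participants had a reaction or how severe it was overall

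*Combined protocol and SAP*

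**What the plan says.** Three parts of the combined protocol and SAP bear on how a reaction to dosing is recorded and reported.

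- **Recording.** Appendix 3 Section 1.1 covers adverse events associated with the infusion or injection that occur during administration or in the following 24 hours. These "should be captured as individual signs and symptoms on the Adverse Event eCRF rather than as an overall diagnosis". The example is to "record dyspnea and hypotension as separate events rather than a diagnosis of infusion-/ injection-related reaction or anaphylactic reaction". Appendix 3 Section 1.2 has the diagnosis recorded for all other events, and lets earlier sign entries be replaced once a diagnosis is made. Appendix 2 Section 3, which covers AEs and SAEs together, says: "Whenever possible, the diagnosis (not the individual signs/symptoms) will be documented as the AE/SAE". It makes no exception for dosing reactions and does not refer to Appendix 3 Section 1.1.
- **Analysis.** The primary AE endpoint in Section 3 is "Frequency and severity of adverse events (AEs), including adverse events of special interest (AESI), serious adverse events (SAE), and treatment discontinuations due to AEs". Section 9.4.2 (Table 11) states: "AEs will be summarized by mapped term and appropriate thesaurus level". The same section names for listing and summary "The safety data, including AEs, injection-site reactions, reasons for withdrawal from study", among other items. Section 8.3.6 does not include infusion reaction or anaphylaxis among the AEs of special interest.
- **Action.** Section 8.3.7 and Table 9 are written for the syndrome. An infusion-related reaction of Grade 2 or above calls for unscheduled safety samples. For anaphylaxis: "If a study drug-related anaphylactic or serious hypersensitivity reaction occurs, administration of RO7565020 should be stopped immediately and permanently discontinued". Section 8.5 asks for an extra PK sample at treatment discontinuation when an infusion-related AE is reported, and gives infusion- or injection-related reaction as the example.

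**The concern.** This is a first-in-human antibody study with safety as its primary objective. Section 8.6 foresees symptomatic hypersensitivity. A footnote to Table 1 adds vital signs every 30 minutes during infusion so that infusion-related reactions can be evaluated. The syndrome is therefore an expected object of study, yet the specific recording rule breaks it into parts and nothing described puts the parts together again.

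Two things are at stake. First, a reader of the safety tables would want to know how many participants in each cohort had a dosing reaction, and of what maximum grade. Under Appendix 3 Section 1.1 the tables cannot say. An empty row for infusion-related or anaphylactic reaction in the first 24 hours would reflect the recording rule and would not be evidence that none occurred. Second, two instructions point in opposite directions for the same event. Sites may follow different ones, so one cohort could mix diagnosis terms and sign terms.

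**Working it through.** **1. The two recording rules side by side.** Take anaphylaxis one hour after dosing. Appendix 2 Section 3 leads to one entry, the diagnosis. Appendix 3 Section 1.1 leads to several entries, the signs, and names this diagnosis as one not to enter. The later-replacement provision in Appendix 3 Section 1.2 does not help, because it applies only to events other than infusion or injection reactions.

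**2. What the tables can recover.** Use the plan's own two signs in a cohort with 6 active participants. Suppose the table shows dyspnea 1/6 and hypotension 1/6. That fits:
- one participant with both signs, as a single reaction: 1/6;
- two participants with one sign each, as two reactions: 2/6;
- two unrelated events and no reaction: 0/6.

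The table is the same in all three cases. Listings could separate the first case from the other two, but they would not show whether the investigator judged the signs to be one reaction or how severe it was overall.

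**3. The plan's own detection figure.** Section 9.2 gives at least an 80% chance of seeing at least one AE at 28% incidence with 5 participants, and at 24% with 6. With P = 1 − (1 − p)^n:
- n = 5, p = 0.28: 1 − 0.72^5 = 0.8065
- n = 6, p = 0.24: 1 − 0.76^6 = 0.8073

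Both reproduce. The statement concerns any AE, so it still holds when a reaction is entered as signs.

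**4. What changes when one sign term stands in for the reaction.** Let the reaction have a true incidence of 24%, and let a given sign term appear in a share s of reactions. The documents give no value for s, so a range is shown. With n = 6, P = 1 − (1 − 0.24s)^6:

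| s (assumed) | 0.24s | Chance of seeing the term at least once |
|---|---|---|
| 1 | 0.24 | 80.7% |
| 0.75 | 0.18 | 69.6% |
| 0.5 | 0.12 | 53.6% |
| 0.25 | 0.06 | 31.0% |

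A reaction-level record corresponds to s = 1.

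**5. The stopping rules.** The first cohort rule in Section 4.1.1.3.1 begins "Severe non-serious adverse reactions (Grade 3 or above, as per Division of AIDS [DAIDS] grading, v2.1". It counts two or more participants with such a reaction judged related to RO7565020, whatever the organ class. At a 24% participant rate, the chance of two or more among 6 is 1 − 0.76^6 − 6 × 0.24 × 0.76^5 = 0.442. Splitting a reaction into signs leaves this unchanged, provided at least one sign in each affected participant is graded 3 or above. The serious-reaction rule and the individual rules in Section 4.1.1.3.2 likewise need no diagnosis term.

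**6. Table 9.** The investigator takes these actions at the time of the event, so they do not wait for an eCRF term. What is missing is a record to check them against afterwards: no described AE entry identifies an infusion-related reaction with its own grade, or an anaphylactic reaction.

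**The case against.** The strongest reply is that the two appendices are a general rule and a specific exception. Section 8.3 sends recording procedures to Appendix 3 and lists infusion and injection reactions apart from other AEs. Appendix 2 Section 3 is qualified by possibility, and Appendix 3 Section 1.1 says should. That is a reasonable reading, but Appendix 2 Section 3 also governs SAEs and gives no pointer to the exception, so the conflict is there for a site to meet.

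It can also be said that little is lost. Each sign is an AE with its own grade, seriousness and causality; injection-site reactions are named for summary; listings would show same-day signs in a small cohort; the PK trigger is any infusion-related AE, which a recorded sign satisfies; and a reaction made of Grade 2 signs already contains Grade 2 events. Serious reactions also come with expedited reports and narrative. All of this stands, and it limits the point. It does not supply a participant-level count or an overall grade for systemic reactions.

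A reader might go further and infer that the primary AE endpoint cannot count or grade these reactions, or that the stopping rules have nothing to work on. The documents do not support either. The endpoint is the frequency and severity of AEs, the signs are AEs, and no reaction-level primary endpoint is defined. The stopping rules count participants with related severe or serious reactions under any term. The remaining gap is narrow: a reaction judged severe as a whole but entered as signs each below Grade 3. The Dose Decision Team's discretionary criterion is available for that case.

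Finally, the eCRF and the Dose Escalation Plan are separate documents that are not available here, so a linking field cannot be excluded.

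**Conclusion.** The point holds in a limited form. Appendix 2 Section 3 and Appendix 3 Section 1.1 give opposite instructions for dosing reactions within 24 hours, including anaphylaxis. If the Appendix 3 rule is followed, the planned tables report the signs but neither the number of participants with a reaction nor its overall severity, and the syndrome-based entries in Table 9 have no matching AE record for verification.

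The size cannot be fixed from the documents, which give no reaction rate or sign pattern. The illustrative fall from 80.7% to between 31.0% and 69.6% rests on an assumed 24% reaction rate and assumed sign shares of 0.25 to 0.75, and it applies only when one sign term is read as the reaction. The primary endpoint can still be computed and the stopping rules still operate. Events that are not infusion or injection reactions, such as later immune-complex reactions, fall under Appendix 3 Section 1.2 and are recorded as diagnoses. This is an inexpensive improvement to the safety reporting and does not invalidate the design. It assumes that no linking field already exists in the eCRF.

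**What to change.** - Reconcile Appendix 2 Section 3, Appendix 3 Section 1.1 and Table 9, so that sites have one instruction for dosing reactions and the exception, if kept, is cross-referenced.
- Add a reaction-level entry (infusion-related, injection-related, or hypersensitivity/anaphylactic), or a flag linking the signs of one reaction, with an overall DAIDS grade, seriousness and causality. Keep the individual signs on a linked page.
- In Section 9.4.2, add a table of participants with at least one reaction, by cohort and maximum reaction grade, counting each participant once. Use the same record to verify the Table 9 sampling and discontinuation entries.

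The cost is appendix wording, one eCRF field or page, and one table. No symptom detail is lost. The stopping rules, their counting unit and the clinical actions are left as they are.
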